1. BACKGROUND AND RATIONALE

Breast milk is essential for premature infants' health and development. However, mothers of preterm infants often experience high stress levels due to the Neonatal Intensive Care Unit (NICU) environment, which can negatively affect milk production and breastfeeding confidence. This study aims to investigate whether Virtual Reality (VR) based relaxation can increase milk volume and self-efficacy.

2. OBJECTIVES

Primary Objective: To compare the daily breast milk volume between the VR intervention group and the control group over three days.

Secondary Objective: To evaluate the effect of VR relaxation on breastfeeding self-efficacy scores.

3. STUDY DESIGN

Type: Randomized Controlled Trial (Parallel Group).

Setting: A Level II Neonatal Intensive Care Unit.

Duration: 3 consecutive days for each participant.

4. PARTICIPANT SELECTION

Inclusion: Primiparous mothers of infants born at 32-35 weeks of gestation, delivered via C-section, willing to express milk.

Exclusion: Systemic/psychiatric diseases, use of galactagogues, or visual/hearing impairments.

Sample Size: 44 participants (22 Intervention, 22 Control).

5. INTERVENTION PROTOCOL

Experimental Group: Participants use a VR headset to watch a 10-minute nature video with classical music in a quiet room. Immediately after, a trained researcher performs manual milk expression for at least 20 minutes.

Control Group: Participants sit in the same quiet room for 10 minutes without VR. Then, the same manual milk expression procedure is performed by the researcher.

Timing: All sessions occur between 12:00 and 14:00 to ensure hormonal consistency.

6. STATISTICAL ANALYSIS PLAN (SAP)

- Data will be analyzed using SPSS software.
- **Descriptive Statistics:** Mean, standard deviation, median, and percentages will be used.
- **Normality Test:** Shapiro-Wilk or Kolmogorov-Smirnov.
- **Comparison:** Mann-Whitney U test for comparing the two independent groups.
- Friedman test for evaluating changes over the 3-day period within groups.
- Spearman's correlation to examine the relationship between variables.
- Significance Level: $p < 0.05$.

Prepared by:

Assistant [name] [name], RM, PhD

Kocaeli University, Faculty of Health Sciences, Midwifery Department

[contact]

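### The SAP does not say how its single between-group test is applied to three days of milk volume, so the primary decision rule and its false-positive rate are not fixed in advance

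*Combined protocol and SAP*

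**What the plan says.** Section 2 (Objectives) sets one primary objective: "To compare the daily breast milk volume between the VR intervention group and the control group over three days". Section 3 (Study Design) gives "Duration: 3 consecutive days for each participant", and section 4 gives "Sample Size: 44 participants (22 Intervention, 22 Control" in each respective arm.

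Three lines of section 6 (SAP) bear on this objective:

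- the between-group line, "Mann-Whitney U test for comparing the two independent groups";
- the line for the repeated days, "Friedman test for evaluating changes over the 3-day period within groups";
- the threshold, "Significance Level: $p < 0.05".

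The between-group line is not attached to any outcome. It is also the only one available for the secondary objective, "To evaluate the effect of VR relaxation on breastfeeding self-efficacy scores". No section defines a mean, total or other single value per mother, names a deciding day, says how many days must be significant, or adjusts for more than one test.

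Section 5 (Intervention Protocol) fixes the clock time, "All sessions occur between 12:00 and 14:00 to ensure hormonal consistency". It does not say whether the daily volume is the yield of that session or the whole day's amount.

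**The concern.** A Mann-Whitney U test takes one value per mother, and this design produces three. To run the primary analysis, someone must choose one day, all days separately, or a summary of the days. The plan leaves that choice until after the data can be seen.

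The Friedman test does not close the gap. It asks whether volume changes over days inside one arm, and neither of its two results is a comparison between arms.

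Two things are at stake. The stated 0.05 threshold is the chance of a false primary claim only under some of the permitted choices. And if the arms differ on one or two days but not on the others, the plan cannot say whether the primary objective was met.

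**Working it through.** **Inputs from the documents.** Three days per mother (section 3), 22 mothers per arm (section 4), Mann-Whitney U test and threshold 0.05 (section 6).

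**Assumptions.** Tests are two-sided, since the SAP does not state sidedness. The correlation r between two days in the same mother is equal for all pairs and is varied from 0 to 0.95, since the documents give no value.

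**The plan's own figures.** The documents give no effect size, SD, power or dropout with the 44, so the sample size cannot be reproduced. It is used here only as the arm size.

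**Step 1: bounds for an any-day rule.** For three independent tests, 1 − (1 − 0.05)³ = 1 − 0.857 = 0.143. Under any dependence the rate is at most 3 × 0.05 = 0.15.

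**Step 2: correlated days.** I simulated 40,000 trials per value of r with no difference between arms. The rank sum W in one arm of n = 22 has mean n(2n + 1)/2 = 22 × 45/2 = 495 and SD √(n²(2n + 1)/12) = √(484 × 45/12) = √1815 = 42.6. A test is significant if |W − 495|/42.6 > 1.96. For Holm, the chance that at least one day passes depends only on whether the smallest p-value is below 0.05/3 = 0.0167, that is, |z| > 2.394.

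| Assumed r | Any day p < 0.05 | All three days p < 0.05 | Holm, at least one day | One test on three-day mean |
|---|---|---|---|---|
| 0 | 14.3% | 0.0% | 4.8% | 5.0% |
| 0.3 | 13.5% | 0.0% | 4.5% | 4.9% |
| 0.5 | 12.6% | 0.2% | 4.4% | 4.9% |
| 0.7 | 10.7% | 0.8% | 3.7% | 4.8% |
| 0.8 | 10.1% | 1.2% | 3.6% | 4.9% |
| 0.9 | 8.6% | 2.0% | 3.1% | 4.9% |
| 0.95 | 7.5% | 2.6% | 2.7% | 5.0% |

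The simulation error near 10% is √(0.1 × 0.9/40,000) = 0.15 percentage points. Because the test uses ranks, the daily-test columns do not depend on the shape of each day's volume distribution.

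**Step 3: what the choice of rule costs in power (illustration only).** Suppose the effect builds as 0, 0.4 and 0.8 SD on days 1, 2 and 3, with r = 0.7 and normal data. Simulated power is 29% for the three-day mean and 55% for Holm (at least one day).

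A rough check uses a normal approximation for a difference in means:

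- *Three-day mean.* The average effect is 0.4 SD. The SD of a three-day mean is √((1 + 2 × 0.7)/3) = √0.8 = 0.894 daily SDs, so the standardised effect is 0.4/0.894 = 0.447. Then 0.447 × √(22/2) − 1.96 = −0.48, or about 32%.
- *Holm, day 3 alone.* 0.8 × √(22/2) − 2.394 = 0.26, or about 60%.

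Both approximations run a little above the simulated values, as expected for a rank test with 22 per arm.

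With a constant effect of 0.8 SD, the same r and normal data, the order reverses: 80% for the mean and 73% for Holm.

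**The case against.** The strongest reply is that the inflation belongs to a rule the documents never state. Section 6 does not say that three tests will be run or that one significant day is enough. A single test on a three-day mean fits the objective equally well and holds about 5%. This stands. A reader might infer from the table that the trial has a false-positive rate of up to 14%, and the documents do not support that. They support only the statement that the rate is not fixed, and that it reaches 8–14% under one permitted rule.

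A reader might also infer that the primary objective must be reworded before a mean can be used. It need not be: a mean daily volume is a fair reading of the objective as written.

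Nor do the figures show that a constant effect always favours the mean. With strongly skewed data (assumed log SD 1.0, constant shift of 0.5 raw SD, r = 0.3), Holm has about 98% power against 94% for the mean. The documents give no distribution, so no general power rule can be offered.

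The session yield is a natural reading of the daily volume, because section 5 describes one expression procedure in one time window. It is still not stated, and a short definition settles it.

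The Mann-Whitney test itself is not at fault. With one value per mother it is a sound choice. Brevity in a small protocol is understandable, but it does not supply a decision rule.

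**Conclusion.** The point holds as an omission with measurable consequences. The plan's only between-arm test is not tied to a day, a per-mother value or an adjustment, so the primary decision rule can be settled after the data are seen.

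At 22 per arm, the false-positive rate is about 8–14% if any significant day counts, below about 3% if all three must be significant, and about 5% for one test on the three-day mean. These figures rest on two-sided tests, equal between-day correlation from 0 to 0.95, and the named decision rule in each case. The absence of a rule is certain from the documents. Which rate would apply is not. The power figures are illustrations on assumed effects and do not show that one remedy is better in general.

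**What to change.** Before the data are examined, state in section 6 that the primary analysis is one two-sided Mann-Whitney U test at 0.05 on each mother's mean daily volume over the days available for her. Define that volume as either the session yield or the whole-day amount. Make the per-day comparisons secondary, with Holm adjustment across the three days, and use the Friedman test only to describe change within an arm. Section 2 can stand as worded.

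An acceptable alternative is Holm across the three daily Mann-Whitney tests as the primary analysis. In that case, state that the objective is met if at least one day passes and that claims are limited to the days that pass.

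The cost is a few sentences of SAP text, with no extra data or participants. With the mean, a difference on a single day can no longer be claimed as the primary result, and power is lower if the effect appears only on later days (29% against 55% in the illustration above). Which option has more power depends on an effect pattern and a distribution that the documents do not give, so the sponsor should choose on the question it wants answered.

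### Self-efficacy (secondary outcome): prespecifying a rank ANCOVA on a score taken before the first session would be a low-cost improvement, worth having if that score correlates about 0.5 or more with the final one

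*Combined protocol and SAP*

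**What the plan says.** Section 2 gives the secondary objective as "To evaluate the effect of VR relaxation on breastfeeding self-efficacy scores". No section names the scale, says when it is given, or mentions a score taken before the first session.

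Section 6 has one method for comparing the arms: "Mann-Whitney U test for comparing the two independent groups". It is not tied to a particular outcome and carries no covariate. The other inferential methods are a "Friedman test for evaluating changes over the 3-day period within groups", which does not compare the arms, and Spearman's correlation, which does not test the arm effect. The significance level is 0.05, with sidedness not stated.

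Section 4 sets 22 mothers per arm, 44 in all, without a power, effect size or standard deviation. Section 3 gives each mother three consecutive days in the study.

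**The concern.** If mothers start with different levels of self-efficacy, an unadjusted comparison of final scores treats that variation as noise. In a trial of 22 per arm this can hide a real effect on the secondary outcome. A score taken before the first session cannot be affected by the intervention, so adjusting for it is legitimate and needs no extra participants. If it is to be used, it has to be collected and written into the SAP beforehand. It cannot be recovered later, and choosing to adjust after seeing the data would be open to challenge.

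**Working it through.** **Plan's own figure.** The sample size of 44 cannot be reproduced, because no power, effect size or SD is given. What 22 per arm can detect can be worked out instead.

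**Inputs.** From the documents: 22 per arm (section 4) and 0.05 (section 6). Assumed: a two-sided test, no dropout, effects of 0.8 SD and 0.5 SD, and r from 0 to 0.7.

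**Step 1: effect detectable with 80% power, no adjustment.** For a comparison of means, √(2/22) × (1.960 + 0.842) = 0.3015 × 2.802 = 0.845 SD. Under normality the relative efficiency of Mann-Whitney is 3/π, so its figure is 0.845 / √(3/π) = 0.845 / 0.977 = 0.864 SD.

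**Step 2: approximate effect of adjustment.** For normal scores the rank correlation is r_s = (6/π) × arcsin(r/2). Adjusting for the ranked pre-score multiplies the error variance of the ranks by 1 − r_s².

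| r | 1 − r_s² | 44 mothers act like 44/(1 − r_s²) | Detectable effect, 0.864 × √(1 − r_s²) |
|---|---|---|---|
| 0 | 1.000 | 44 | 0.86 SD |
| 0.3 | 0.917 | 48 | 0.83 SD |
| 0.5 | 0.767 | 57 | 0.76 SD |
| 0.7 | 0.534 | 82 | 0.63 SD |

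**Step 3: simulation of the two analyses.** Scores were generated as Y = rX + √(1 − r²)e + d × arm, with X and e standard normal, 22 per arm and 100,000 trials per setting. Method A is the Mann-Whitney test on Y. Method B is rank ANCOVA: rank Y and X over all 44 mothers, fit rank(Y) = a + b × arm + c × rank(X), and test b with a t statistic on 44 − 3 = 41 degrees of freedom.

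| r | A, d = 0.8 | B, d = 0.8 | Gain (points) | A, d = 0.5 | B, d = 0.5 |
|---|---|---|---|---|---|
| 0 | 71.4% | 70.7% | −0.7 | about 35% | 34.7% |
| 0.2 | 71.0% | 72.0% | +1.0 | about 35% | 35.8% |
| 0.3 | 71.1% | 74.0% | +2.9 | about 35% | 36.9% |
| 0.5 | 71.2% | 81.0% | +9.8 | about 35% | 42.7% |
| 0.7 | 71.1% | 92.1% | +21.0 | about 35% | 56.2% |

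With d = 0, both methods rejected in 4.9% to 5.1% of trials.

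**Step 4: two checks.** Quade's form of rank ANCOVA (10,000 trials per setting, d = 0.8) gave 71 / 74 / 82 / 92% at r = 0 / 0.3 / 0.5 / 0.7. With scores rounded to steps of 0.1 SD and capped at assumed ceilings (1.8 SD above the pre-score mean, 1.2 SD above the control final mean), Mann-Whitney gave about 70% and rank ANCOVA 69 / 70 / 73 / 80 / 91% at r = 0 / 0.2 / 0.3 / 0.5 / 0.7. Neither check changes the pattern.

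**The case against.** The strongest reply is that the benefit rests on a correlation found nowhere in the documents. At r = 0.2 to 0.3 the gain is 1 to 3 points at 0.8 SD, and at r = 0 there is a small loss. This stands, and it is why the gain is stated conditionally.

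A second reply is that the change may need new data collection as well as new SAP wording, since no pre-session score is described. This also stands, though the burden is one questionnaire per mother.

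Four stronger readings are tempting, and the documents support none of them:

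- *The Mann-Whitney test is wrong.* It is not. Under randomisation, one such test at one time point holds its 5% level. That assurance covers a single test only. If the arms were compared on each of the three days, the chance of at least one false positive would be about 11% to 13% (assumed between-day correlations of 0.7 to 0.5). The plan does not say how many self-efficacy comparisons will be made.
- *The protocol itself says that mothers differ at the start.* Section 1 describes stress from the NICU environment, "which can negatively affect milk production and breastfeeding confidence". That describes an exposure shared by mothers in one unit and does not say how they differ from one another before the first session. Starting differences are plausible but assumed.
- *The plan compares change scores between arms.* It does not say so. The changes mentioned in section 6 belong to the within-group Friedman test.
- *Milk volume needs the same adjustment.* No document shows that any baseline variable predicts volume, and the eligibility criteria already narrow the range of gestational age, parity and mode of delivery. No claim is made for the primary outcome.

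**Conclusion.** This is an optional improvement to a secondary analysis. The listed test is valid, but it makes no use of a pre-session score, and none is described. At an assumed 0.8 SD effect the gain is about 10 points of power at r = 0.5 and 21 at r = 0.7. At 0.5 SD it is about 8 and 21 points. Below r of about 0.5 the gain is too small to matter much, and at r = 0 the loss is under 1 point. These figures assume 22 analysed mothers per arm, a two-sided 0.05 test and approximately normal scores (similar under the assumed ceiling). The effect sizes and correlations are assumptions, so the documents settle the direction of the argument but not the size of the benefit.

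**What to change.** 1. If it is not already planned, give the self-efficacy scale once before the first session and before the mother learns her arm. A score taken before the day 2 or day 3 session will not serve: treatment has started by then, and adjusting for it could remove part of the effect.
2. In section 6, prespecify one analysis of self-efficacy at one stated time point: a linear model of the ranked final score on arm and ranked pre-score, two-sided at 0.05, with the pre-score as the only covariate.
3. Keep the unadjusted Mann-Whitney test of the final score as a sensitivity analysis, and report medians by arm beside the model, because the arm coefficient is in rank units and has no direct clinical meaning.
4. If any mothers have already been enrolled without a pre-score, the adjusted analysis cannot be applied to them, and the Mann-Whitney test should stay as the analysis.

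If made before enrolment, the change costs a few lines of SAP text and, where no pre-score is planned, one short questionnaire per mother. Ranking and a one-covariate linear model can be run in the SPSS software that the plan already names.

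### The only association analysis is a plain Spearman correlation with no allowance for arm, so pooling the 44 mothers could turn a VR effect on both outcomes into an apparent link between them

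*Combined protocol and SAP*

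**What the plan says.** The statistical analysis plan (section 6) has a single line on association: "Spearman's correlation to examine the relationship between variables". It sits in the same list as the 0.05 significance threshold. It does not say which variables are meant, which day or summary of milk volume is used, whether the arms are combined, or how three days per mother are handled.

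The line before it is more specific about arm: "Friedman test for evaluating changes over the 3-day period within groups". The Spearman line carries no such limit.

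Section 2 gives two outcomes. The primary objective is "To compare the daily breast milk volume between the VR intervention group and the control group over three days"; the secondary is "To evaluate the effect of VR relaxation on breastfeeding self-efficacy scores". Section 1 expects VR to act on both: "This study aims to investigate whether Virtual Reality (VR) based relaxation can increase milk volume and self-efficacy". Section 3 adds "Duration: 3 consecutive days for each participant", and section 4 sets 22 mothers per arm. How often self-efficacy is measured is not stated.

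**The concern.** Because the Friedman line is restricted by group and the Spearman line is not, the natural reading is one correlation across all 44 mothers. If VR moves both outcomes upward, the pooled data consist of two groups displaced in the same direction. A rank correlation picks up that displacement, even if self-efficacy says nothing about milk volume among mothers in the same arm.

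A significant coefficient could then be reported as showing that more confident mothers produce more milk, or as support for a mechanism, when it only restates the treatment effect.

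A second, separate question is the unit of analysis. Three daily volumes per mother make it possible to enter 3 × 44 = 132 rows. Ordinary Spearman would treat those rows as independent.

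**Working it through.** **Inputs from the documents.** 22 mothers per arm; three days each; threshold 0.05 (taken as two-sided, since sidedness is not stated); VR expected to raise both outcomes.

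**Assumptions, because the documents give no figures.** Normal data; no association within arms; VR shifts of d1 and d2 within-arm standard deviations on the two outcomes; a range of within-mother correlations.

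**The plan's own figure.** No number is given for the correlation analysis. The total of 44 cannot be reproduced, because no effect size, standard deviation, power or dropout is stated. For scale only: 80% power at two-sided 0.05 for a difference in means needs n per arm = 2(1.96 + 0.8416)²/d². At d = 0.85 this is 15.70/0.7225 = 21.7, or 22. So 22 per arm suits a shift of about 0.85; power at d = 0.5 is 38%.

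**Step 1: the induced correlation.** With equal arms, the arm indicator has variance 1/4. The pooled covariance is therefore d1·d2/4 and each pooled variance is 1 + d²/4, giving

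r = (d1·d2/4) / √[(1 + d1²/4)(1 + d2²/4)].

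- Equal shifts of 0.8: 0.16/1.16 = 0.138.
- Equal shifts of 0.86: 0.185/1.185 = 0.156.
- Shifts of 0.86 and 0.4: 0.086/√(1.185 × 1.04) = 0.077.
- Either shift zero: r = 0.

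**Step 2: rejection rates, one value per mother (n = 44), 10,000 simulated trials per row.**

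| Shift on both outcomes | r from formula | Mean Spearman | Pooled rejection | Arm-adjusted rejection |
|---|---|---|---|---|
| 0 | 0.000 | 0.00 | 5.2% | 5.3% |
| 0.3 | 0.022 | 0.02 | 5.2% | 4.9% |
| 0.5 | 0.059 | 0.05 | 5.9% | 4.8% |
| 0.8 | 0.138 | 0.14 | 15.0% | 4.8% |
| 1.0 | 0.200 | 0.20 | 26.4% | 4.9% |
| 1.2 | 0.265 | 0.28 | 45.1% | 5.3% |
| 1.5 | 0.360 | 0.38 | 74.7% | 5.3% |
| 0.5 on one outcome only | 0.000 | 0.00 | 5.3% | 5.3% |

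Repeat simulations gave 6–7% at 0.5, 17–18% at 0.86, 44% at 1.2 and 74% at 1.5, and about 7% for unequal shifts of 0.86 and 0.4. Spearman within a single arm (n = 22) rejected 4.6% to 5.3% of the time.

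**Step 3: 132 mother-days entered as independent rows, no VR effect, 4,000 simulated trials per setting.** The mean coefficient is about zero, but rejection rises.

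| Within-mother correlation | Self-efficacy measured daily | One self-efficacy score repeated |
|---|---|---|
| 0.5 | 10.1% | 16.4% |
| 0.7 | 16.5% | 19.5% |
| 0.9 | 23.3% | 24.9% |

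A shared day trend of 0.5 SD per day in both outcomes, with within-mother correlation 0.5 and no VR effect, gave a mean coefficient of 0.14 and 39% rejection.

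**The case against.** The strongest reply is that the analysis criticised is not written down. The plan names no variable pair, does not say the arms are pooled and does not say days are stacked. A within-arm Spearman on one value per mother also fits its wording and has no such distortion. This stands: the plan leaves the error open and its wording leans towards pooling, but it does not commit to it.

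A second reply is that the pooled test is not invalid. If VR shifts both outcomes, they really are associated in the combined sample, and rejecting the hypothesis of no marginal association is correct. This also stands. The rates in Step 2 are rejections of a hypothesis of no association within arms, so the harm lies in interpretation.

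Third, a reader might infer that the problem arises whenever the trial succeeds. The documents do not support that. The primary objective concerns milk volume alone, and a shift in only one outcome induces no correlation. Nor does anything in the documents support shifts of 1.2 or 1.5 on both outcomes at once; those rows only show how the effect grows.

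Fourth, the repeated-days problem should not be presented as a consequence of a VR effect. It needs none, and it depends on a data layout the plan does not mention.

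Finally, neither stated objective relies on the correlation. That limits the point's importance, but it does not excuse leaving a tested analysis open to two readings with different error behaviour.

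**Conclusion.** The point holds in a conditional form and is minor. If the Spearman analysis is run on milk volume and self-efficacy with the arms pooled, a material VR effect on both outcomes can produce a correlation that is absent within arms. With equal shifts, the distortion is negligible up to d = 0.5, about 14–18% rejection at 0.8 to 0.86, and 44–45% at 1.2. Allowing for arm brings it back to about 5% at every shift tried. Independently, stacking mother-days would give roughly 10–25% false positives for within-mother correlations of 0.5 to 0.9.

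These sizes rest on assumed shifts, within-mother correlations, normality and a two-sided test, none of which the documents supply. The primary and secondary between-arm comparisons are not affected, so this should not be read as a threat to the trial's main conclusions.

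**What to change.** Replace the Spearman line in section 6 with: *The association between milk volume and self-efficacy will be examined with one value per mother (for example the 3-day mean volume) using a partial Spearman correlation controlling for study arm, with arm-specific Spearman correlations also shown; mother-days will not be treated as independent observations; the result is exploratory.* If another pair of variables is intended, name it in the same form, and state which self-efficacy measurement is used.

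Reporting by arm alone would also remove the distortion, but with only 22 mothers per coefficient; the partial correlation keeps all 44. The 3-day mean is one reasonable summary among several.

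The cost is one degree of freedom (41 instead of 42) and slightly more analysis work. In SPSS it can be done by ranking both variables and running a partial correlation on arm. No new data are needed.
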